7.4 Exploratory Efficacy Analyses

[Redacted]

[Redacted]

[Redacted]

Protocol 31-201-301 Interim Analysis Plan

7.4.1.1 Statistical Methods

The variables relating to hospitalization data will be compared between the 3 months of the retrospective versus the corresponding prospective periods using McNemar test; similar comparisons will be done for Month 1-6 as well.

The number and cumulative or mean duration of psychiatric hospital stays (or treatment visits) will be summarized using descriptive statistics and compared between the SOC by paired t-test between the retrospective and corresponding prospective periods.

Continuous variables in the form of change from baseline will be summarized by the descriptive statistics (n, mean, median, standard deviation (SD), standard error (SE), maximum, minimum) and tested using the paired t-test for Efficacy Sample and Completer Sample separately. The frequency and percentage will be provided for the variables of discontinuation rate [redacted] based on the Efficacy Sample and Completer Sample.

The Kaplan-Meier estimate of the median discontinuous time and the overall Kaplan-Meier curve for efficacy sample will be provided for the time-to-discontinuation due to all causes.

Protocol 31-201-301 Interim Analysis Plan

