3.3 Trial Population

The trial population will include male and female subjects, 18 to 65 years of age, inclusive, with a diagnosis of schizophrenia according to DSM-5 criteria. Subjects must have had at least 1 inpatient psychiatric hospitalization within 4 years (48 months) prior to screening. Subjects must have been prescribed oral antipsychotic treatment for at least 6 months or longer prior to screening. Approximately 493 subjects will be screened in order to enroll 320 subjects and complete 224 subjects.

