3.10 Definition of Completed Subjects

The treatment period is defined as the time period during which subjects are evaluated for primary and/or secondary objectives of the trial irrespective of whether or not the subject actually received all doses of Abilify MyCite. For the purposes of this trial, subjects who complete the Month 6/ET visit will be defined as treatment completers. Subjects who are

Protocol 031-201-00301

evaluated at the last scheduled visit during the treatment period will be defined as trial completers.

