7.2 Datasets for Analysis

The safety dataset includes all subjects that were administered at least one dose of Abilify MyCite.

The following analysis samples are defined for this trial:

- Enrolled Sample: comprises all subjects who sign an eICF for the trial.
- Prospective Safety Sample: comprises all subjects who receive at least one dose of Abilify MyCite in the prospective phase.
- Efficacy Sample: the core dataset for all efficacy analyses is the modified Intent-to-Treat (mITT) dataset which will consist of data from all subjects entering the prospective phase who have completed the first 3-months of dosing on Abilify MyCite. However, as will be described below, in order to handle missing data and restrictions imposed by different types of analyses (eg, change from baseline analysis), other datasets derived from the ITT dataset will be used for the efficacy analyses.

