5.1 Data/Data Sets Specifications

5.1.1 Data Sets Analyzed

The following analysis samples are defined for this study:

Enrolled Sample: comprises all subjects who sign an eICF for the trial and entered screening.

Safety Sample: comprises all subjects who receive at least one dose of study medication in the prospective phase.

Protocol 31-201-301 Interim Analysis Plan

Intent-to-Treat Sample: consists of all Enrolled Sample who met the study inclusion/exclusion criteria and who are intended to receive study medication in the prospective phase.

Modified Intent-to-Treat (mITT): dataset which will consist all ITT subjects entering the prospective phase who have taken at least 80% of the study medication for the specified analysis period, and had complete information on hospitalization during the specified analysis period; that is for the Month 1-3 mITT: the specified period will be Month 1-3 prospective/respective; for the Month 4-6 mITT and Month 1-6 mITT, the specified period will be Month 4-6 prospective/respective and Month 1-6 prospective/respective, respectively.

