7.1.3 Sensitivity Analyses

As sensitivity analysis, the primary efficacy analysis will be performed on the mITT subjects who have completed the 3-month treatment only that is all subjects who are in study for at least 75 days (12 weeks adjusting for the 9 days allowed for visit window).

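### All-cause discontinuation is to be analysed in a sample that, on either available definition, leaves out subjects who stop in about the first 67 to 84 days

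*SAP*

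**What the plan says.** SAP 7.4.1.1 plans two summaries of discontinuation. For time to discontinuation from all causes, "The Kaplan-Meier estimate of the median discontinuous time and the overall Kaplan-Meier curve for efficacy sample will be provided". The frequency and percentage for the discontinuation rate are "based on the Efficacy Sample and Completer Sample"; the words directly after the rate are blacked out.

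SAP 5.1.1 defines four sets: Enrolled, Safety, ITT and mITT. It defines no Efficacy Sample and no Completer Sample. The texts that could supply a meaning are these:

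- **Efficacy Sample, Protocol 7.2.** It is equated with the protocol's mITT dataset: "all subjects entering the prospective phase who have completed the first 3-months of dosing on Abilify MyCite".
- **mITT, SAP 5.1.1.** ITT subjects entering the prospective phase "who have taken at least 80% of the study medication for the specified analysis period", with complete hospitalization information for that period.
- **Completers, SAP 7.1.3.** For a sensitivity analysis of the primary endpoint, mITT subjects who completed 3 months of treatment, explained as "all subjects who are in study for at least 75 days".
- **Completers, Protocol 3.10.** "subjects who complete the Month 6/ET visit will be defined as treatment completers".

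The Safety Sample in SAP 5.1.1 "comprises all subjects who receive at least one dose of study medication in the prospective phase". Figure 5.1 in the SAP's list of outputs is the Kaplan-Meier curve of all-cause discontinuation; its title names no sample.

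**The concern.** A time-to-discontinuation analysis should start with everyone who started treatment. Here, membership of the sample is decided by the outcome: a subject who stops early enough is not in the set in which stopping is counted. The early part of the curve is then fixed by the definition and carries no information, and the median and the rate inherit the same selection.

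Early stopping is foreseeable in this trial. Protocol 3.7 and 3.8.3.1 provide for subjects whom the investigator judges, by Day 14, unsuited to continue on the product. The secondary endpoint is adherence, so a reader will look to the retention curve as supporting evidence. A curve that is flat for the first two to three months because of how the sample was chosen could be mistaken for good early retention.

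**Working it through.** **1. The plan's own numbers.** The documents give no figure for the discontinuation analysis. The planning figures are the only guide to size.

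Protocol 7.1 starts from 200 completed subjects (80% power, two-sided alpha 0.05, paired difference d = 0.085, discordant proportion ψ = 0.185). The McNemar formula gives

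n = (1.960·√ψ + 0.8416·√(ψ − d²))² / d² = (1.960 × 0.4301 + 0.8416 × 0.4216)² / 0.007225 = 198.6, so 199.

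That reproduces the 200. The increase to 224 for the interim looks was not re-derived, since nothing here depends on it.

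Protocol 7.1 ties the 224 to completing the 3-month treatment, and Protocol 3.3 says "Approximately 493 subjects will be screened in order to enroll 320 subjects and complete 224 subjects". Hence 320 − 224 = 96 do not complete, 96/320 = 30%, and 224/320 = 70%.

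**2. When the curve can first fall.** Months are 28 days, so Months 1 to 3 are 84 days.

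- *Protocol 7.2 definition:* completion of 3 months of dosing is required, so the estimate is 100% up to about Day 84.
- *SAP mITT, Month 1-3 version:* 0.80 × 84 = 67.2. With one dose a day, nobody who stops before about Day 67 can qualify, so the estimate is 100% up to then. A stop between about Day 68 and Day 84 could count. (The Month 1-6 version would need 0.80 × 168 = 134.4 days.)

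This holds whether the event is stopping the product or leaving the trial, because either one before those days prevents the required dosing.

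**3. Contrast at Day 84.** Assume that 320 are treated and that all 96 non-completers discontinue by Day 84.

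- *Safety Sample:* 96/320 = 30% discontinued, 70% retained.
- *Efficacy Sample (Protocol 7.2):* none of the 96 is included, so 100% are retained by construction.

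**4. Carry-over to Day 168.** This needs an assumption: a constant discontinuation hazard h = −ln(1 − p)/84, where p is the proportion stopping by Day 84. Among all treated, 1 − (1 − p)² have stopped by Day 168. Among those who reached Day 84, the proportion is 1 − (1 − p)²/(1 − p) = p. The medians are ln 2/h and 84 + ln 2/h.

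| p by Day 84 | Stopped by Day 168, all treated | Stopped by Day 168, Efficacy Sample | Median, all treated | Median, Efficacy Sample |
|---|---|---|---|---|
| 10% | 19% | 10% | Day 553 | Day 637 |
| 20% | 36% | 20% | Day 261 | Day 345 |
| 30% | 51% | 30% | Day 163 | Day 247 |
| 40% | 64% | 40% | Day 114 | Day 198 |

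Medians beyond Day 168 are extrapolations; in the trial they would be reported as not reached. At p = 30% the choice of sample turns a median of about Day 163 into one that is not reached.

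If the 224 were instead 6-month completers, constant hazard gives Day 84 retention of √0.70 = 84% against 100%, and 30% stopped by Day 168 against 1 − 0.70/0.837 = 16%.

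Constant hazard ignores the planned treatment decision at Month 3, so the Day 168 figures are only illustrative. The Day 84 contrast in step 3 does not use it.

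**The case against.** The strongest reply is that the SAP may mean ITT. SAP 7.2 puts the paired t-test for PDC on the prospective-phase efficacy sample, yet the matching outputs (CT-5.2.1, CT-5.2.2, listing EFF-1.5) are labelled ITT. SAP ITT membership rests on eligibility and intention to treat, so it would keep early dropouts. Protocol 7.2 also allows other datasets derived from ITT. This shows that the term is used inconsistently. It does not supply a definition that displaces Protocol 7.2, and no ITT-derived set is named for this analysis.

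Second, parts of SAP 7.4 and the exploratory endpoint list are blacked out, so an event definition or a population stated there cannot be seen. That is a fair limit on certainty. The visible sentence nevertheless names the efficacy sample for the curve.

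Third, early dropout is reported elsewhere: study duration and reasons on enrolled subjects (SAP 6.1), reasons on ITT (CT-2.1), exposure on the Safety Sample (CT-7.1, CT-7.2), discontinuations due to adverse events on the Safety Sample (CT-8.5.1), and a listing of discontinued subjects (DREAS-1). This stands, and it limits the harm. Those outputs do not give a time-to-event estimate, and their counts would sit beside a curve that disagrees with them.

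Fourth, choosing the Safety Sample over ITT is partly preference. ITT would also keep early dropouts, but it can include subjects never dosed, for whom a Day 1 origin is unclear. Protocol 3.5.4 lists all-cause discontinuation among the safety endpoints, which favours the Safety Sample.

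**Conclusion.** Wrong as written, and not only a missing definition: both texts that define an efficacy or mITT set select on staying on treatment. The planned curve, its median and the Efficacy Sample rate omit discontinuations in about the first 67 days (SAP mITT) to 84 days (Protocol 7.2). The 100% against 70% at Month 3 rests on the Protocol 7.2 definition and on all 96 non-completers being early discontinuations. The 224 are described as evaluable, so some of the 96 could be subjects who stayed but were not evaluable.

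A reader might infer more than the documents support:

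- *That no discontinuation can ever appear in these samples.* Month 4 to 6 stops still count in the Efficacy Sample.
- *That the rate in the Completer Sample is zero by construction.* No such sample is defined. Under the 75-day rule, later stops count. Under the Month 6/ET wording, a withdrawn subject who attends the early-termination visit could qualify as a completer.
- *That the report conceals dropout.* The outputs listed under the objection show it.
- *That the plan assumes 30% dropout.* That figure is only implied by 224/320.

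The analysis is exploratory and descriptive, and the primary McNemar test is not affected by this section.

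**What to change.** In SAP 7.4.1.1, run the discontinuation rate and time to all-cause discontinuation on the Safety Sample, with time counted from Day 1, and name that sample in the title of Figure 5.1. Drop the Completer Sample for the discontinuation rate.

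Elsewhere, replace Efficacy Sample and Completer Sample with sets defined in SAP 5.1.1. This includes the change-from-baseline tests in 7.4.1.1 and the PDC test in SAP 7.2, whose tables are already labelled ITT. If a completer set is still wanted for other analyses, define it there.

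The cost is SAP wording and the population flag in the affected outputs. No new data are needed.

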7.4.1.2 Technical Details

Number of inpatient psychiatric hospital stays per subject during the 3 months (Months 1-3) of the retrospective (or prospective) period is determined as the total number of inpatient psychiatric hospitalization, closed (locked) ward or open ward, but not primarily for psychosocial reasons for each subject during the respective/retrospective periods. Cumulative duration of inpatient psychiatric hospitalization per subject is the sum of duration of each reported inpatient psychiatric hospitalization for each subject, which is defined as $\min(\text{Date of Discharge, End date of the 3-months of the respective period}) - \max(\text{Start Date of Admission, Start date of the 3-months of the respective period}) + 1$. Mean duration of inpatient psychiatric hospitalization per subject is derived as the cumulative duration divided by the number of inpatient psychiatric hospitalization for each subject. If a subject did not experience any inpatient psychiatric hospitalization during the 13-months, zero will be assigned to his/her number of inpatient psychiatric hospital stays, and to his/her cumulative and mean duration of inpatient psychiatric hospitalization. Similarly, method will be used to analyze the cumulative duration of inpatient psychiatric hospitalization and mean duration of inpatient psychiatric hospitalization during Month 1-6.

Inpatient hospitalizations for psychosocial reasons are defined as inpatient psychiatric hospitalization, closed (locked) ward or open ward, where hospitalization is primarily psychosocial reasons. For the last 3 months (Months 4-6) of the retrospective (or prospective) period, number and cumulative or mean duration of inpatient hospitalizations for psychosocial reasons are derived in similar ways to those of inpatient psychiatric hospitalization.

Number and cumulative or mean duration of inpatient non-psychiatric hospitalizations during the 3 months (Months 1-3) of the retrospective (or prospective) period are derived in similar ways to those of inpatient psychiatric hospitalization.

Psychiatric partial hospitalization program, psychiatric intensive outpatient program or psychiatric assertive community treatment program are reported in their corresponding category in the CRF panel of psychiatric non-inpatient treatment visits. For each category of the program, number of programs during the 3 months (Months 1-3) of the retrospective (or prospective) period can be determined by their number of occurrences during the respective period. Duration (i.e., the total number of stays/sessions) of each program is derived as the product of the mean number of stays/sessions attended per week (as recorded in CRF) and the overall length of the program in weeks, rounded to the smallest following integer. For both retrospective and prospective periods, the overall length of each program defined as $\min(\text{Program End Date, End date of the 3 months of}$

Protocol 31-201-301 Interim Analysis Plan

the respective period) – max(Program Start Date, Start date of the 3-months of the respective period) + 1. For each subject, cumulative duration for each category of the programs is the sum of duration of each program in that category and mean duration is the average over all reported programs in that category.

Number of psychiatric emergency visit, psychiatric outpatient treatment visit, nonpsychiatric emergency room visit, nonpsychiatric urgent care facility visit, or nonpsychiatric outpatient visit can be determined from their reported occurrences in the category of emergency room and/or outpatient treatment visits from CRF. Psychiatric outpatient treatment visit will include such visits with a psychiatrist (MD) provided in a private doctor’s office, with a psychiatrist (MD) provided in a hospital outpatient clinic, or of other type. Nonpsychiatric outpatient visit will include such visits with a medical doctor provided in a private doctor’s office, with a medical doctor provided in a hospital outpatient clinic, or of other type.

For endpoints in the form of change from baseline, baseline definitions are provided in [Section 5.1.2](#).

[Redacted content]

Protocol 31-201-301 Interim Analysis Plan

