7.1 Sample Size

The primary endpoint of this trial compares the paired proportions of inpatient psychiatric hospitalization during the retrospective period (Month 1 to 3) and the prospective period (Month 1 to 3), which will be analyzed using a McNemar test.

Based on published results of other similar studies for the particular time periods (retrospective Month 1 to 3 and prospective Month 1 to 3)^{23,24} we are evaluating, it is reasonable to assume that 15.5% of subjects are hospitalized during retrospective Month 1 to 3 and 7% are hospitalized during prospective Month 1 to 3; about 5% of subjects who are not hospitalized retrospective will be hospitalized prospective, while 13.5% of subjects who are hospitalized retrospective will not be hospitalized. With this assumption, 200 completed subjects will provide 80% power (alpha = 0.05 two-sided) to detect a difference of 8.5% in 2 paired hospitalization proportions between pre-switch and post-switch periods while the proportion of total discordant pairs is 18.5%. In addition, this sample size will provide 80% power for the comparison of retrospective Month 4 to 6 vs prospective Month 4 to 6, assuming 30% of the subjects are hospitalized pre-switch (12.5% subjects will be hospitalized post-switch and another 17.5% won't have hospitalization post-switch) and, overall, 20% are hospitalized post-switch (among them, 12.5% subjects are hospitalized both pre-switch and post-switch and 7.5% have no hospitalization pre-switch).

Two interim analyses are planned at when 50% and 70% of subjects have completed the prospective period (Month 1 to 3); in order to conserve the overall Type I error at 0.05 level, 224 to 300 evaluable subjects are needed to complete the 3-month treatment to maintain 80% power. This sample size assumes the 3 sequential tests are made using LanDeMets Spending Function²⁵ with O'Brien-Fleming boundary, a futility conditional power of 15% is built in the sample size calculation to allow the trial to stop for futility. Based on the conditional power and the alpha level at the interim analysis, the trial could stop for efficacy or futility, continue with initially planned 224 sample size or increase to up to 300 if the conditional power fall between 30% to 80% (Section 7.4.4). The 2-sided alpha levels for these 2 interim analyses are 0.00312 and 0.0139 respectively, and the alpha left for the final analysis will be 0.04528.

Protocol 031-201-00301

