Appendix 2 Table of Contents for Proposed Tables and Listings**Summary Tables:**

- CT-1.1 Subject Disposition by Site (Enrolled Sample)
- CT-2.1 Reasons for Discontinuation (ITT Sample)
- CT-2.2 Discontinuation from treatment / study due to COVID
- CT-3.1.1 Demographic Characteristics by Gender and Site and Overall (ITT Sample)
- CT-3.1.2 Demographic Characteristics by Gender and Site and Overall (Month 1-3 mITT)
- CT-3.2.1.1 Baseline Disease Characteristics by Gender and Site and Overall (ITT Sample)
- CT-3.2.2.1 Baseline Disease Characteristics by Gender and Site and Overall (Month 1-3 mITT)
- CT-4.1.1 Medications Taken Prior to Start of Trial (Safety Sample)
- CT-4.2 Medications Taken During Trial (Safety Sample)
- CT-4.3 Medications Taken Post Trial (Safety Sample)
- CT-4.4.1 Listing of ConMeds due to COVID
- CT-4.4.2 Summary of Protocol Deviations (ITT Sample)

Protocol 31-201-301 Statistical Analysis Plan

CT-5.1.1 Analysis of Inpatient Psychiatric Hospitalization Rate Between the Retrospective Period Month 1-3 and the Prospective Period Month 1 - 3 (Month 1-3 mITT)

CT-5.1.2 Analysis of Inpatient Psychiatric Hospitalization Rate Between the Retrospective Period Month 1-3 and the Prospective Period Month 1 - 3 (ITT Sample)

CT-5.1.3 Analysis of Inpatient Psychiatric Hospitalization Rate Between the Retrospective Period Month 1-3 and the Prospective Period Month 1 - 3 (Month 1-3 mITT and Completer)

CT-5.1.2.1 Number of Inpatient Psychiatric Hospital Stays Per Subject Between Retrospective Period and Prospective Period Month 1-3 (Month 1-3 mITT)

CT-5.1.2.2 Number of Inpatient Psychiatric Hospital Stays Per Subject Between Retrospective Period and Prospective Period Month 1-3 (ITT Sample)

CT-5.1.2.3 Cumulative Duration of Inpatient Psychiatric Hospitalization Per Subject Between Retrospective Period and Prospective Period Month 1-3 (Month 1-3 mITT)

CT-5.2.3.4 Cumulative Duration of Inpatient Psychiatric Hospitalization Per Subject Between Retrospective Period and Prospective Period Month 1-3 (ITT Sample)

CT-5.1.2.5 Mean Duration of Inpatient Psychiatric Hospitalization Per Subject Between Retrospective Period and Prospective Period Month 1-3 (Month 1-3 mITT)

CT-5.1.2.6 Mean Duration of Inpatient Psychiatric Hospitalization Per Subject Between Retrospective Period and Prospective Period Month 1-3 (ITT Sample)

CT-5.2.1 Summary of PDC for Month 1-3 Retrospective/Prospective Period (ITT Sample)

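### Mean duration of hospitalization is set to zero for subjects with no admission, so it falls when fewer subjects are admitted even if length of stay is unchanged

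*SAP*

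**What the plan says.** SAP 7.4.1.2 (Technical Details) gives three per-subject quantities for each 3-month period: number of stays, cumulative duration and mean duration. The third is a ratio: "Mean duration of inpatient psychiatric hospitalization per subject is derived as the cumulative duration divided by the number of inpatient psychiatric hospitalization for each subject". For subjects without an admission, "zero will be assigned to his/her number of inpatient psychiatric hospital stays, and to his/her cumulative and mean duration of inpatient psychiatric hospitalization". The condition that triggers the zero is worded "If a subject did not experience any inpatient psychiatric hospitalization during the 13-months", a length that matches no period in this trial. The same method is carried over to Months 1 to 6.

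SAP 7.4.1.1 (Statistical Methods) says: "The number and cumulative or mean duration of psychiatric hospital stays (or treatment visits) will be summarized using descriptive statistics". It adds that they are "compared between the SOC by paired t-test", retrospective against prospective.

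SAP Appendix 2 lists a per-subject table of mean duration for the Month 1-3 mITT sample (CT-5.1.2.5) and for the ITT sample (CT-5.1.2.6). The Interim Analysis Plan, Appendix 1, lists it as CT-5.1.3.3. No visible text restricts any length-of-stay summary to subjects who were admitted.

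**The concern.** Zero is the true value for the number of stays and for total days of a subject who was never admitted. It is not a length of stay: the ratio is 0/0. Once the gap is filled with zero, the average over all subjects is the probability of any admission multiplied by the average stay of those admitted. The variable then moves with the share of subjects admitted, which the primary endpoint already measures, while its name points to length of stay.

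What is at stake is interpretation. A fall in this table could be read as shorter stays when stays had not changed, or had even become longer.

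**Working it through.** **Inputs.** From Protocol 7.1: "15.5% of subjects are hospitalized during retrospective Month 1 to 3 and 7% are hospitalized during prospective Month 1 to 3", and "about 5% of subjects who are not hospitalized retrospective will be hospitalized prospective". The same section gives 13.5% admitted retrospectively only, so 15.5% − 13.5% = 2% are admitted in both periods (check: 5% + 2% = 7%). N is 200 without and 224 with the two interim analyses. The documents give no stay length. I assume the same stay-length distribution in both periods, with mean L = 7 to 21 days and coefficient of variation (CV) 0 to 1.5.

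**Step 1: reproduce the plan's figure.** For the McNemar test with d = 0.135 − 0.05 = 0.085 and discordant share 0.185:

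N = [1.960 × √0.185 + 0.842 × √(0.185 − 0.085²)]² / 0.085² = 198.6, so 199.

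Power at N = 200 is 80.3%. The stated 200 subjects and 80% are reproduced, so the admission rates are read as the plan meant them.

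**Step 2: share of zeros.** 100% − 15.5% = 84.5% of retrospective values and 100% − 7% = 93% of prospective values would be assigned zeros.

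**Step 3: expected zero-filled mean duration, stay length unchanged.** Expected value = P(admitted) × L.

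| L (days) | Retrospective, 0.155 × L | Prospective, 0.07 × L |
|---|---|---|
| 7 | 1.09 | 0.49 |
| 10 | 1.55 | 0.70 |
| 14 | 2.17 | 0.98 |
| 21 | 3.26 | 1.47 |

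The relative fall is 1 − 0.07/0.155 = 54.8% in every row, because L cancels.

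**Step 4: how much longer stays would have to be to hide the fall.** The break-even ratio is 0.155/0.07 = 2.21. If prospective stays were twice as long, the variable would still fall by 1 − 2 × 0.07/0.155 = 9.7%.

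**Step 5: the paired t-test.** I simulated 8,000 trials per setting with cells 2% / 13.5% / 5%, one stay per admitted subject, gamma stay lengths with the same distribution in both periods, and two-sided 0.05. The entries are the share of trials with a significant fall.

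| CV of stay length | N = 224 |
|---|---|
| 0 | 86% |
| 0.5 | 76% |
| 0.6 | 72% |
| 0.8 | 63% |
| 1.0 | 54% |
| 1.5 | 37% |

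The t statistic does not depend on the unit of length, so L does not matter here; only the spread does. Stays were not cut off at the end of the 84-day period.

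**Step 6: restricted to admitted subjects.** The expected value is L in both periods, so the difference is 0. At CV 0.5 to 1, a Welch test among admitted subjects rejected in about 5% to 6% of simulated trials, close to nominal. Expected numbers at N = 224: 0.155 × 224 ≈ 35 retrospective, 0.07 × 224 ≈ 16 prospective, and 0.02 × 224 ≈ 4.5 in both.

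**The case against.** The SAP states the zero rule openly and titles the tables as per-subject. The variable it defines really does differ between periods, so the rejections in Step 5 are not Type I errors for that variable. This stands: the fault is in the name and what it suggests, not in the validity of the t-test. Likewise, 54.8% is the plan's assumed incidence effect restated (8.5/15.5). It shows that the variable says nothing separate about stay length; it is not an independent measure of harm.

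Number of stays and cumulative days are tabulated alongside, and subject-level hospitalization listings are planned, so a careful reader could separate incidence from length. That reduces the risk of misreading but does not make the mean-duration table informative.

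A reader might infer three stronger points that the documents do not support.

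- **That any fall in the number of admissions produces the artefact.** It does not. A subject who goes from two equal stays to one keeps the same mean, because the SAP divides by the number of stays. The effect comes only from fewer subjects having any admission. How closely the variable copies cumulative duration depends on how many subjects have repeat stays, which the documents do not state.
- **That the sponsor will claim shorter stays as a separate benefit.** No visible text says so, and the wording of the exploratory endpoints is redacted.
- **That the interim decisions are exposed because the table is in the interim report.** Section 4 of the Interim Analysis Plan ties the decision strictly to its Table 2-1, which uses the p-value and conditional power from the McNemar analysis of the primary endpoint.

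**Conclusion.** The concern holds as a problem of definition and labelling in an exploratory outcome. The 54.8% rests only on the plan's admission rates and on equal average stay length in the two periods. The 37% to 86% range also rests on one stay per admitted subject and on an assumed CV of 1.5 down to 0; no single value in it can be preferred from the documents.

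The outcome falls under SAP 7.4 (Exploratory Efficacy Analyses), so the primary conclusion does not change. The point is minor, but worth correcting before the tables are read as evidence on length of stay.

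The trigger wording needs correction in any case. Read literally, the 13-month condition would leave a subject admitted in only one period with an undefined value in the other. The 3-month period is the evident meaning, since the paragraph defines 3-month quantities.

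**What to change.** In SAP 7.4.1.2:

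- Treat mean duration as not applicable for a subject with no admission in the period.
- Keep zero for number of stays and cumulative duration.
- Replace the 13-month reference with the relevant 3-month period (deleting it would leave the sentence incomplete), and use the 6-month period where the method is carried to Months 1 to 6.

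In SAP 7.4.1.1, drop the paired t-test for mean duration and report it descriptively, with n, among subjects admitted in each period. Keep the paired comparison for number of stays and cumulative days. A paired test limited to subjects admitted in both periods would rest on about 4 to 5 of 224 and would carry little information. Align the mean-duration tables in SAP Appendix 2 and in the Interim Analysis Plan.

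The cost is SAP wording and table footnotes; no new data are needed. There is a statistical downside: the descriptive comparison is unpaired, rests on about 35 against 16 subjects, and conditions on being admitted. If milder admissions are the ones prevented, average stay among the rest would rise. The table should carry that caveat.
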